An electrocardiogram (ECG) will be performed at Baseline/Week 1, Week 7, Week 12, and then every 12 weeks. An echocardiogram (ECHO) will be performed at Week 12, and then every 24 weeks. Clinical laboratory assessments will be performed at Baseline/Week 1, Weeks 2-9, and Week 12, then every 4 weeks to Week 36, and then every 12 weeks. Vital signs will be assessed weekly pre- and post-infusion. Height will be assessed every 12 weeks. Weight will be assessed at Baseline/Week 1, and then every 4 weeks. A full physical examination will be conducted at Baseline/Week 1, Week 4, Week 12, Week 24, and then every 24 weeks. A brief physical examination will be conducted every 4 weeks (except at times of a full physical examination) to Week 36, and then every 24 weeks. Patients will undergo additional physical examinations, ECGs, clinical laboratory assessments and CCI during the first 8 weeks of open-label treatment.

DURATION OF STUDY:

Screening Period: up to approximately 4 weeks

Double-Blind Dose-Titration with Open-Label Extension: up to 144 weeks

Post-treatment Follow-Up Period: approximately 4 weeks

Total duration of patient participation: approximately 152 weeks

NAME OF COMPANY Sarepta Therapeutics, Inc. [name] [contact]	NAME OF FINISHED PRODUCT SRP-4045 Injection
	NAME OF ACTIVE INGREDIENT SRP-4045
NUMBER OF PATIENTS: 12 patients (8 SRP-4045 + 4 placebo)	
INCLUSION CRITERIA:	
Patients must meet all of the following inclusion criteria to be eligible for this study.	

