^c Before patients may begin open-label treatment, safety laboratory assessments must be performed within 2 weeks prior to first dose. If safety laboratory samples were collected more than 2 weeks prior to the first open-label extension visit, samples must be collected again and results must be reviewed before dosing.

[figure not shown]

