8.3. Completion of a Patient's Participation and Overall Study Completion

The length of a patient's participation in the double-blind dose-titration period of the study will be from the time that the informed assent/consent forms are signed until approximately 4 weeks after the last patient enrolled in the study received 12 weekly doses of double-blind treatment. Based upon the findings of the DSMB in its review of dose-titration safety data, the Sponsor will determine whether to roll over patients onto open-label treatment with SRP-4045 at 30 mg/kg (or the highest tolerated dose as determined during the dose titration). Treatment will continue until Study Week 144, such that the last patient enrolled will have received approximately 128 weeks of open-label SRP-4045.

After completion of treatment, patients will return for a post-treatment safety visit approximately 4 weeks after their last study infusion. The study will end once the last patient has completed his last study visit.

Follow-up for end of study is applicable for patients who complete Study 4045-101, but who do not choose to participate in the LTE study. A safety follow-up visit will occur approximately 4 weeks after the last study infusion at the end of study or for early termination. Follow-up for

early termination is required for patients who discontinue prematurely from Study 4045-101. Patients who complete Study 4045-101 per protocol and who roll over to the LTE study will not require a follow-up visit for Study 4045-101.

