10.3.3. Clinical Laboratory Assessments

All laboratory assessments, with the exception of PK sampling, must be performed prior to dose administration for all treatment visits.

Routine clinical laboratory testing will occur according the schedule of events during the dose-titration and extension study period ([Table 2](#)) and the open-label introduction study period ([Table 3](#)). The assessments in [Table 3](#) will occur during the first 8 weeks of the open-label treatment period and are in addition to the assessments in [Table 2](#). In the case of a duplicate assessment specified by [Table 2](#) and [Table 3](#) at the same study visit, only one assessment should be performed.

During Screening, safety laboratory assessments must be performed within 2 weeks prior to the Baseline/Week 1 visit, and results must be reviewed prior to dosing. If Screening safety laboratory samples were collected more than 2 weeks prior to the Baseline/Week 1 visit, samples must be collected again and results must be reviewed before patients may be dosed at Baseline/Week 1.

Before patients may begin dosing in the open-label extension period, safety laboratory assessments must be performed within 2 weeks prior to first dose, and the results of those labs reviewed prior to first dose. If safety laboratory samples were collected more than 2 weeks prior to the first open-label extension visit, samples must be collected again and results must be reviewed before dosing.

Laboratory results will be analyzed by an accredited central laboratory selected by the Sponsor (Sarepta Therapeutics). Assessments and shipment will be prepared according to the Laboratory Manual provided for the study. Specific laboratory parameters to be analyzed are presented in the subsections below.

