### **4.3.2. Blinding of Treatment**

This study includes a double-blind, placebo-controlled dose-titration period of at least 12 weeks during which all patients, parents, Investigators, and site staff not involved with drug product preparation will be blinded to treatment assignment. A double-blind, placebo-controlled study design will be used to reduce potential bias during data collection and evaluation of outcome parameters. Eight patients will receive weekly IV doses of SRP-4045, and 4 patients will receive weekly IV doses of placebo in a blinded fashion until approximately 4 weeks after the last enrolled patient received 12 weeks of treatment. Only individuals (ie, the qualified pharmacist and back-up pharmacists) who are authorized to verify dose and dose assignment will be unblinded to treatment assignment. These individuals will not interact with study participants and will be instructed not to divulge randomization assignment to others under any circumstances, unless directed to do so by the Investigator in the interest of patient safety.

During the open-label extension period, treatment assignment at the double-blind period will remain blinded until final database lock for the final data analysis.

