## 5. GENERAL STATISTICAL METHODS AND CONVENTIONS

### 5.1. General Methods

For continuous variables, descriptive statistics will include the number of patients with data to be summarized (n), mean, standard deviation (SD), median, minimum, and maximum.

For categorical/qualitative variables, descriptive statistics will include frequency counts and percentages. The total number of patients in a treatment group will be used as the denominator for percentage calculations, unless stated otherwise.

Unless stated otherwise, summaries of all endpoints will be by treatment group (see below for definitions of treatment groups) for 3 "Analysis Periods" (Double-Blind Period, Casimersen Period and Combined Double-Blind and Open-Label Periods):

Double-Blind Period: Data will include all assessments and events that occurred prior to the first dose of 30 mg/kg of casimersen in the open-label period. The analyses for the double-blind period will be primarily for safety.

Double-blind Period analysis treatment groups are:

- patients who received placebo during the double-blind Period
- patients who received casimersen at 4 mg/kg (Weeks 1-2), 10 mg/kg (Weeks 3-4), 20mg/kg (Weeks 5-6), and 30mg/kg (Weeks 7-8)
- <=20 mg/kg during Week 1 to 6 (only used for select endpoints)
- patients who received casimersen at 30 mg/kg during Weeks 7 to the end of the double-blind period
- patients who received casimersen at any dose level during Weeks 1 to the end of the double-blind period

Casimersen Period: For AEs and other safety-related data analysis, data will include all assessments and events that occurred while patients received casimersen. Assessments and events that occurred in the double-blind period for patients who were on placebo during the double-blind period will be excluded. Assessments and events that occurred during the double-blind period for patients who received casimersen will be included.

Casimersen Period Analysis treatment group is:

- all casimersen treated patients: Patients who receive casimersen in any portion of the study

Combined Double-blind and Open-label Periods: For efficacy data analysis, data will include all assessments and events during both treatment periods of the study.

Combined Double-blind and Open-label Periods Analysis treatment groups are:

- Placebo-Casimersen: Patients who receive placebo in the double-blind period followed by casimersen in the open-label period

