#### **Duration of Treatment**

Duration of casimersen treatment will be calculated as the duration in weeks from the date of first dose of casimersen to the date of the last casimersen administration as recorded on the STUDY DRUG ADMINISTRATION eCRF plus 6 days, (ie, last dose date - first dose date + 1 + 6)/7. Similarly, duration of casimersen treatment at dose  $\leq 20$  mg/kg will be calculated as the duration in weeks from the date of first dose of casimersen to the date of the last casimersen administration at dose level  $\leq 20$  mg/kg + 6 days. Duration of casimersen treatment at dose of 30 mg/kg will be calculated as the duration in weeks from the date of first dose of casimersen at 30 mg/kg to the date of the last casimersen administration at dose level of 30 mg/kg + 6 days. Duration of placebo treatment will be calculated as the duration in weeks from the date of first dose of placebo to the date of the last placebo administration + 6 days.

The duration in weeks calculated above will then be categorized to 1 of the following intervals: < 24, 24 to < 48, 48 to < 72, 72 to < 96, 96 to < 120, or  $\geq 120$ .

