#### **6.8.4. Clinical Laboratory Evaluation**

A shift table will present the number and percentage of patients in each cell resulting from cross-tabulating the status (low, normal, and high) of the highest/lowest post-baseline value versus that of the Baseline for each laboratory test, if applicable, by analysis period and treatment group as defined in Section 5.1. If a specific test can have both a significant low and high, then a shift table will be generated for each direction. The percentage will be based on the total number of patients in the Safety Set. A status of missing may be added, if necessary. This analysis will be repeated for last post-baseline result.

Only the highest value will be summarized for alanine aminotransferase (ALT), alkaline phosphatase, amylase, aspartate aminotransferase (AST), C-reactive protein, creatine kinase, creatinine, cystatin C, gamma glutamyl transferase (GGT), lactate dehydrogenase (LDH), total bilirubin, uric acid, absolute basophils, absolute eosinophils, basophil percent, eosinophil percent, activated partial thromboplastin time, international normalized ratio, prothrombin time, and urine KIM-1, and urine protein. Only the lowest value will be summarized for albumin, and platelets. Both the highest and lowest values will be summarized for blood urea nitrogen (BUN), calcium, chloride, glucose, potassium, sodium, absolute lymphocytes, absolute monocytes, absolute neutrophils, hematocrit, hemoglobin, lymphocyte percent, monocyte percent, neutrophils percent, white blood cell (WBC) count, and urine pH and specific gravity.

The frequency and percentage of patients meeting the potentially clinically significant abnormality criteria (defined in [Appendix Table 1](#), [Appendix Table 2](#), [Appendix Table 3](#)) at any time point post-baseline will be summarized by Analysis Period and treatment group. Additionally, the total number of potentially clinically significant abnormalities will be summarized.

Baseline value, highest/lowest value and last observation and the corresponding change from Baseline will be summarized by Analysis Period and treatment group.

All patient-level clinical laboratory values will be displayed in data listings. In addition, values meeting the potentially clinically significant abnormalities criteria will be presented in data listings. Treatment-emergent abnormalities will be indicated in the listing.

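### The double-blind 30 mg/kg group starts at Week 7 by study week, so the Week 7 pre-infusion lab, taken after 20 mg/kg only, can be counted under 30 mg/kg

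*SAP*

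**What the plan says.** SAP 5.1 lists the double-blind treatment groups. One is "patients who received casimersen at 30 mg/kg during Weeks 7 to the end of the double-blind period". Unlike the pooled group at or below 20 mg/kg (Weeks 1 to 6), it is not restricted to selected endpoints. The same list also shows the individual dose levels, with 30 mg/kg given as Weeks 7-8.

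SAP 6.8.4 refers to the 5.1 groups for its shift tables. It says that abnormalities "at any time point post-baseline will be summarized by Analysis Period and treatment group". SAP 5.7 places serially collected values in a study week according to the eCRF page.

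On timing, Protocol 10.3.3 states: "All laboratory assessments, with the exception of PK sampling, must be performed prior to dose administration for all treatment visits". The Protocol synopsis gives the schedule: "Clinical laboratory assessments will be performed at Baseline/Week 1, Weeks 2-9, and Week 12, then every 4 weeks to Week 36". Protocol Table 2 puts the first 30 mg/kg infusion at Week 7.

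The SAP has one date-based definition tied to 30 mg/kg. Under Duration of Treatment in 5.8, time on that dose runs "from the date of first dose of casimersen at 30 mg/kg to the date of the last casimersen administration" at that level. It serves exposure, not the attribution of safety data.

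**The concern.** A lab drawn before the Week 7 infusion can reflect exposure up to 20 mg/kg and nothing higher. The 5.1 group opens at Week 7 rather than at the first 30 mg/kg infusion, so a literal reading files that lab under a dose not yet given. No passage says how an assessment is assigned to a dose level within the titration.

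The incidence of laboratory abnormalities is part of the primary safety endpoint (Protocol 7.3). Protocol 9.8.1 expects the most likely drug-related events to be renal and monitors them largely by laboratory tests. With at most 8 casimersen patients per column, one misfiled abnormality is visible in a percentage.

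**Working it through.** There is no plan figure to reproduce, because the analysis is descriptive. The check compares the dose implied by the week label with the last dose infused before each pre-infusion lab.

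**Inputs**
- Dose by week (SAP 4.1, Protocol Table 2): 4 mg/kg in Weeks 1-2, 10 in Weeks 3-4, 20 in Weeks 5-6, 30 from Week 7.
- Post-baseline labs (Protocol synopsis): Weeks 2-9 and 12, then every 4 weeks to Week 36.
- Casimersen patients: 8.
- End of the double-blind period: SAP 4.3.2 has blinded dosing continue "in a blinded fashion until approximately 4 weeks after the last enrolled patient received 12 weeks of treatment". For the last patient enrolled that is 12 + 4 = 16 weeks. Protocol 8.3 agrees. Treatment runs to Week 144 "such that the last patient enrolled will have received approximately 128 weeks of open-label SRP-4045", and 144 − 128 = 16.

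**Dose by week label against last dose infused (mg/kg)**

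| Lab week | By week label | Last infused |
|---|---|---|
| 2 | 4 | 4 |
| 3 | 10 | 4 |
| 4 | 10 | 10 |
| 5 | 20 | 10 |
| 6 | 20 | 20 |
| 7 | 30 | 20 |
| 8, 9, 12, 16 | 30 | 30 |

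Within the 30 mg/kg group, only Week 7 is mismatched.

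**Share of scheduled labs in the 30 mg/kg group** = 1 / (number of labs from Week 7 to the end of the period)
- End near Week 16: Weeks 7, 8, 9, 12, 16, so 1/5 = 20%.
- Protocol Table 3 also schedules a lab at open-label Week 1, and its footnote says "Before patients may begin open-label treatment, safety laboratory assessments must be performed within 2 weeks prior to first dose". That sample precedes the first open-label dose, and SAP 5.1 counts everything before that dose as double-blind. If it is a separate draw, the share is 1/6 = 17%.
- Enrolled 4, 8 or 12 weeks before the last patient (assumed), so ending near Weeks 20, 24 or 28: 1/6 = 17%, 1/7 = 14%, 1/8 = 12.5%. With a separate open-label Week 1 draw: 1/7 = 14%, 1/8 = 12.5%, 1/9 = 11%.
- Individual 30 mg/kg column (Weeks 7-8), if used for labs: 1/2 = 50%.

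**Effect on a reported percentage.** SAP 6.8.4 counts a patient on any post-baseline value. A patient abnormal in this group only at Week 7 adds 1/8 = 12.5 points, if all 8 reach 30 mg/kg.

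**Tables affected.** The Week 7 value can enter the highest/lowest-value shift tables, the extreme-value summaries and the any-time abnormality counts. It cannot be the last value if any later double-blind lab exists, so last-value summaries are then unchanged.

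**Vital signs.** Each infusion visit has one reading before and three after the infusion. Weeks 7 to 16 give 10 × 4 = 40 readings, of which the Week 7 pre-infusion reading is 1/40 = 2.5%.

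**Does a date rule help?** The 5.8 definition starts on the date of the first 30 mg/kg dose. If it were borrowed for safety data, a lab drawn earlier that day would still fall inside. A lab drawn on a previous day would be excluded by date but not by week label. The documents do not say that lab and infusion share a date. Table 2 shows only that they belong to the same weekly visit.

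**The case against.** **A 30 mg/kg lab column may not be produced.** The adverse event sections (SAP 6.8.1 to 6.8.3) ask for the 5.1 groups and add dose level for the double-blind period. The lab and vital-sign sections (6.8.4, 6.8.5) omit that addition, and 6.7 drops individual dose levels for exposure. This stands in part: the lab columns are not settled. But 6.8.4 points to the 5.1 groups, and the 30 mg/kg group is one of them without restriction.

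**The wording allows the correct result.** The group consists of patients who received 30 mg/kg, and nearby rules are anchored to a dose: baseline, treatment-emergent lab abnormality and the end of the double-blind period. The eCRF-page rule concerns presentation by time point, not group assignment. A careful programmer could therefore place the Week 7 lab correctly. That is fair, but none of those rules marks the boundaries between dose levels, and no passage states the dose-anchored reading.

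**The columns are confounded anyway.** Each patient is titrated through every dose, so dose is tied to time and cumulative exposure, and moving one lab does not cure that. This is true and limits the importance of the point. It does not justify reporting a finding under a dose not yet given.

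**Stronger readings to resist.** A reader might infer that labs are also lost from the group at or below 20 mg/kg, giving a 25-point swing (12.5 out of one column, 12.5 into the other). That requires labs to be among that group's selected endpoints, which no passage says, and no abnormality at Weeks 2-6. A reader might also infer that 3 of 9 post-baseline labs through Week 12 (Weeks 3, 5 and 7; 33%) are mislabelled. That requires lab tables by individual dose. The Protocol synopsis speaks of tabulation by dose, but SAP 6.8.4 does not repeat it.

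**Conclusion.** The point holds as a minor gap in specification. Applied as written, the week bounds put a lab taken after 20 mg/kg only into the 30 mg/kg column. It makes up 17% to 20% of that group's scheduled labs for a patient ending near Week 16, and about 11% to 17% for patients assumed to have enrolled 4 to 12 weeks earlier. The possible effect is 12.5 points per patient whose only abnormality in that group is at Week 7. These shares describe scheduled samples. They are not predicted changes in any result.

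The conclusion rests on three conditions: a 30 mg/kg column is produced for labs, the group is programmed by week (or by date with a same-day draw), and the schedule is followed. If the SAP's authors intend no such column, the lab part falls away.

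It would be wrong to infer that the primary safety comparison is compromised. The placebo and any-dose casimersen groups and the casimersen-period summaries hold the same data under either attribution. The listings, the DSMB review and the stopping rules do not depend on these columns.

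**What to change.** In SAP 5.1, define each dose-level window from the first infusion of that level to the first infusion of the next level, or to the first open-label dose. Attribute each safety assessment to the most recent infusion begun before it. Treat scheduled same-day labs and pre-infusion vital signs as pre-dose, as Protocol 10.3.3 and the vital-sign schedule already imply. In SAP 6.8.4, state which double-blind dose columns apply to labs.

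Under this rule the Week 7 lab leaves the 30 mg/kg group, which then starts with the Week 8 lab.

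The cost is a few sentences and minor programming. Visit and timepoint labels are enough for scheduled labs and vital signs, so clock times are not needed. Dates alone would not do where the lab and the infusion fall on the same day. Neither dosing nor data collection changes.

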¹ All patients will receive open-label treatment with SRP-4045 at 30 mg/kg (or the highest tolerated dose as determined during the dose titration) administered weekly. Infusions are to be given according to instructions in the Pharmacy Manual. Note that an implanted venous access port may be inserted for treatment administration at the discretion of the Investigator. Patients are to be closely monitored for at least 1 hour following the completion of all infusions. If the patient has not experienced an infusion reaction after 48 weeks of open-label treatment, the Investigator has discretion to reduce the post-infusion observation period to 30 minutes.

^j Home infusions may take place 3 out of every 4 weeks, with the fourth week conducted at the study site. This schedule is intended to reduce study burden while maintaining ongoing in-person surveillance by the study site. Detailed instructions for in-home dosing will be provided in a separate manual to the visiting nurse.

Table 3: Schedule of Events: Introduction of Open-Label Treatment

Note: Open-label treatment may commence once the DSMB has reviewed double-blind dose-titration safety data and the Sponsor's decision has been made to proceed. The assessments in [Table 3](#) will occur during the first 8 weeks of the open-label study period and are in addition to the assessments in [Table 2](#). Duplicate assessments at the same study visit should not be performed.

	OPEN LABEL INTRODUCTION							
	Study week will vary for each patient such that the Open Label Week 1 will be the patient's next scheduled visit after the DSMB review and Sponsor determination of weekly open-label dose level							
Open Label Week	OL W1	OL W2	OL W3	OL W4	OL W5	OL W6	OL W7	OL W8
Full Physical Examination ^a	X			X				
Brief Physical Examination ^b								X
12-lead ECG	X		X					
Clinical Laboratory Assessments	X ^c	X	X	X	X	X	X	X
CCl								

DSMB=Data Safety Monitoring Board; ECG=electrocardiogram; OL=open label; W=week.

[figure not shown]
^a Full physical examination to include review of general appearance, head, eyes, ears, nose, and throat (HEENT), heart, lungs, abdomen, skin, lymph nodes, musculoskeletal, and neurological systems.

^b Brief physical examination will include examination of general appearance, HEENT, heart, chest, abdomen, and skin.

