## 4. STUDY DESCRIPTION

### 4.1. Study Overview

This is a first-in-human, multicenter, randomized, double-blind, placebo-controlled, dose-titration study designed to assess the safety, tolerability, and PK of once-weekly IV infusions of casimersen in advance-stage patients with genotypically confirmed Duchenne muscular dystrophy (DMD) with an eligible deletion amenable to exon 45 skipping (eg, 12-44, 18-44, 44, 46-47, 46-48, 46-49, 46-51, 46-53, or 46-55).

Twelve patients will be randomized (2:1) in double-blind fashion to receive SRP-4045 (n=8) or placebo (n=4). Patients will receive a once-weekly IV infusion of SRP-4045 or placebo at escalating dose levels, each for at least 2 weeks: 4 mg/kg at Weeks 1-2; 10 mg/kg at Weeks 3-4; 20 mg/kg at Weeks 5-6; and 30 mg/kg beginning at Week 7. During the dose titration period of the study, dosing will be interrupted or halted if specific predefined stopping criteria are met, or if interruption is otherwise warranted at the discretion of the Sponsor or Investigator. Once the last patient has received 2 infusions at 30 mg/kg (Week 8), an independent Data Safety Monitoring Board (DSMB) will review cumulative safety data. Review by the DSMB is necessary for advising the Sponsor about whether the safety data allow for longer-term dosing with SRP-4045. Patients will continue to receive their randomized treatment (SRP-4045 or placebo) in a blinded fashion until the DSMB review is complete. Based on the results of this review, the Sponsor will determine whether to roll over the patients into the open-label extension period. During the open-label extension, patients will receive SRP-4045 at 30 mg/kg (or the highest tolerated dose as determined during the dose titration) administered weekly. All activities for these subjects will be outlined in a LTE study protocol.

CCI

[figure not shown]
[figure not shown]

Figure 1: Study Schematic

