## **4.2. Sample Size and Power**

Sample size for this study is based upon qualitative considerations; no formal sample size calculations will be performed. The anticipated sample size is 12 total patients (8 casimersen and 4 placebo) in double-blind period and the same 12 patients will receive SRP-4045 in the open-label period). The selected sample size is considered sufficient to provide initial safety evaluation of SRP-4045 and to provide adequate data to allow for estimation of PK parameters.

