## **6.8. Safety Analyses**

Safety analyses by Analysis period and treatment groups described in Section 5.1 (double-blind period and casimersen period) will include summaries of the following:

- the type, frequency, severity, timing, and relationship to the study drug of AEs, SAEs, and discontinuations due to AEs. Adverse events will be coded using the Medical Dictionary for Regulatory Activities (MedDRA 17.1 and will be reported by primary system organ class (SOC) and preferred term (PT)).
- safety laboratory testing including hematology, coagulation, serum chemistry, and urinalysis
- vital signs
- physical examinations
- 12-lead ECGs
- ECHOs

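### The Casimersen Period safety tables have one pooled group, so the 4 former placebo patients, who start casimersen untitrated, are not shown separately from the 8 titrated patients

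*SAP*

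**What the plan says.** SAP 5.1 sets up three analysis periods. The Casimersen Period has one treatment group: "all casimersen treated patients: Patients who receive casimersen in any portion of the study". Two rules decide what enters it. For the placebo arm: "Assessments and events that occurred in the double-blind period for patients who were on placebo during the double-blind period will be excluded". For the casimersen arm: "Assessments and events that occurred during the double-blind period for patients who received casimersen will be included". The column therefore holds titration plus open-label data for 8 patients, and open-label data only for 4.

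The split by randomised sequence exists in the same section, but under the Combined Double-Blind and Open-Label Periods, which 5.1 introduces for efficacy. One of its groups is "Placebo-Casimersen: Patients who receive placebo in the double-blind period followed by casimersen in the open-label period".

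SAP 6.8 names the periods used for safety: "Safety analyses by Analysis period and treatment groups described in Section 5.1 (double-blind period and casimersen period". The text on adverse events of special interest (AESIs, printed under 6.8.2) and Section 6.8.3 refer instead to every analysis period.

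On dosing, SAP 4.1 and Protocol 7.1 take the casimersen arm through 4, 10, 20 and 30 mg/kg. At rollover the footnotes to Protocol Table 2 put all patients on 30 mg/kg or the highest dose tolerated in titration. The visible text describes no second titration for former placebo patients. The note to Protocol Table 3 says that its extra laboratory tests, ECGs and examinations "will occur during the first 8 weeks of the open-label study period and are in addition to the assessments in" Table 2.

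**The concern.** The two randomised sequences meet the drug in different ways. Eight patients are stepped up over six weeks to 30 mg/kg, and four begin at the open-label dose. The Double-Blind tables show the stepped start by dose level (SAP 6.8.1). No specified table shows the matching first exposure of the other four without mixing in something else.

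Safety is the primary objective, and Protocol 5.4 says that the study will inform the dose for later trials. Infusion-related reactions are an AESI, and for these the type of start is plainly relevant. A reaction confined to the untitrated patients would be diluted by a denominator of 12, and a reader of the tables could not tell which sequence it came from.

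The Table 3 visits raise the same issue. They apply to all patients, but only for the former placebo patients are they the first weeks on casimersen. SAP 6.8.4 reduces laboratory data to baseline, extreme and last values, shifts and abnormality counts, so no specified table treats those visits as an introduction period.

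**Working it through.** **Inputs.** Allocation is 2:1, with 8 casimersen and 4 placebo (SAP 4.1): 8 + 4 = 12 and 8/4 = 2, as stated. There is no power figure to reproduce, since SAP 4.2 says "no formal sample size calculations will be performed". The documents give no event rates, so the counts below are illustrative.

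**Composition of the column.** 4/12 = 33.3% untitrated and 8/12 = 66.7% titrated. If x of the 4 have an event and none of the 8 do, the table shows x/12 in place of x/4, which is one third of the rate.

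**Split against pooled, with exact (Clopper-Pearson) 95% intervals.**

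| Former placebo (n=4) | Titrated (n=8) | Pooled column (n=12) |
|---|---|---|
| 2/4 = 50.0% (6.8 to 93.2) | 0/8 = 0% (0 to 36.9) | 2/12 = 16.7% (2.1 to 48.4) |
| 0/4 = 0% (0 to 60.2) | 2/8 = 25.0% (3.2 to 65.1) | 2/12 = 16.7% (2.1 to 48.4) |
| 1/4 = 25.0% (0.6 to 80.6) | 0/8 = 0% (0 to 36.9) | 1/12 = 8.3% (0.2 to 38.5) |
| 2/4 = 50.0% (6.8 to 93.2) | 1/8 = 12.5% (0.3 to 52.7) | 3/12 = 25.0% (5.5 to 57.2) |

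A pooled 2/12 fits splits of 2+0, 1+1 or 0+2, and the table cannot separate them.

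**Can the split be recovered by subtraction?** Patients count once per preferred term (SAP 6.8.1). For a given term, let A be titrated patients with the event in the double-blind period, B titrated patients with it first in the open-label period, and C former placebo patients with it on casimersen. The Casimersen Period column shows A + B + C and the Double-Blind any-dose casimersen column shows A. The difference is B + C, not C. For example, pooled 3 and double-blind 1 leave B + C = 2, so C may be 0, 1 or 2.

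**Would a Combined Period column do it?** If the AESI and 6.8.3 tables were also run on that period, a Placebo-Casimersen column would appear. It would include events from the placebo months, so it would still not isolate first exposure to casimersen.

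**What n=4 can show.** The chance of at least one event among 4 is 1 − (1 − p)^4:
- p = 10%: 1 − 0.9^4 = 34.4%
- p = 25%: 1 − 0.75^4 = 68.4%
- p = 50%: 1 − 0.5^4 = 93.8%

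For 0/4, the upper 95% limit is 1 − 0.025^(1/4) = 60.2%.

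**Comparability of the first 8 weeks on casimersen.** The titrated patients' scheduled doses average (4+4+10+10+20+20+30+30)/8 = 128/8 = 16 mg/kg. The former placebo patients receive 30 mg/kg throughout (or the highest tolerated dose). The first window is double-blind, the second is open-label and comes later.

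**The case against.** The strongest reply is that nothing is hidden. SAP 5.9 sorts listings by treatment sequence and shows Casimersen Day as appropriate. All adverse events are listed, as are all laboratory, vital-sign, ECG and ECHO values (6.8.1, 6.8.4 to 6.8.6). With four patients, every early event can be read off directly. This stands: a reader might infer that the untitrated-start data cannot be seen, and the documents do not support that. What is missing is a specified summary table.

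A reader might also infer that exposure is pooled in the same way. It is not: SAP 6.7 summarises exposure by period and group and adds casimersen duration categories for the Combined Period, whose groups are the sequences. The size of the difference in duration is also not fixed by the documents. Protocol 8.3 and 9.9.2 imply 12 + 4 = 16 blinded weeks and 144 − 16 = 128 open-label weeks for the last patient enrolled. The synopsis and Protocol 7.1 give about 12 blinded weeks, which would leave 144 − 12 = 132.

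A third tempting reading is that splitting by sequence gives a randomised comparison of titrated with untitrated starts. It does not, because dose, blinding and calendar time all differ between the two windows.

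Finally, an untitrated start is not a stated study question, the primary endpoint is double-blind safety, analyses are descriptive, and SAP 5.6 declines subgroups because of size. These points limit how much weight the split can bear. They do not justify leaving it out: the sequences are the randomised groups, the SAP already defines them, and tallying listings by hand is a poor substitute for a prespecified table.

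**Conclusion.** The point holds as a gap in presentation. In the Casimersen Period safety tables, 4 patients with one type of start and 8 with another share a single column of 12, and no specified casimersen-only safety summary table separates them. An event confined to the 4 appears at one third of its rate, and opposite splits can give the same pooled percentage.

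This rests on the visible text for the absence of titration at rollover, since some of the dose rationale and design text is redacted. It also rests on reading SAP 6.8 as limiting safety to two periods. The wording under 6.8.2 and in 6.8.3 leaves that open, but the alternative reading would not isolate first exposure either. The event counts are illustrative. The split would support coarse description only, and the point concerns reporting: it takes no position on the dosing scheme.

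**What to change.** 1. Present the Casimersen Period adverse event, AESI, laboratory, vital-sign and ECG/ECHO summaries as Placebo-Casimersen (n=4), Casimersen-Casimersen (n=8) and Overall, using the groups already defined in SAP 5.1.
2. Add a descriptive summary of the first 8 weeks on casimersen for the former placebo patients, drawn from their Table 3 visits, beside the existing double-blind titration columns. State in the table that the comparison is descriptive and confounded by dose, blinding and calendar time.
3. Reconcile SAP 6.8, which names two periods for safety, with the text under 6.8.2 and in 6.8.3, which refers to every analysis period.

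No separate exposure request is needed, because the Combined Period summary in 6.7 already covers the sequences.

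The cost is two columns in existing tables and one new table. SAP 5.8 already defines Casimersen Day 1 and a Casimersen Period baseline, and the final analysis follows database lock and unblinding (4.5.2), so no new data or derivation is needed and the blind is not affected. The drawback is small cells: with 4 and 8 patients, percentages move in steps of 25 and 12.5 points, and an empty cell of 4 excludes very little.
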